## 5 CRITERIA FOR EVALUATION

### **5.1 Primary Efficacy Endpoint**

Primary Outcome: The primary outcome will be fluvastatin AUC0-12h and AUC0-∞.

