## 4 STUDY DESIGN

### 4.1 Study Overview

The effect of rifampin on the pharmacokinetics of fluvastatin will be studied in healthy volunteers in a two-period, randomized, unblinded, crossover clinical trial. On period 1 of the study, subjects will be randomized to one of two treatment groups:

- (i) one oral dose of fluvastatin (Lescol®) 20mg capsule
- (ii) one oral dose of fluvastatin (Lescol®) 20mg capsule immediately following a 30-min intravenous infusion of rifampin 600mg in 10ml Normal Saline.

The two study periods will preferentially be on a Tuesday and Thursday, separated by one day of washout. Subjects will be instructed to fast overnight the day before study periods 1 and 2, and for 3h post-dosing. In both treatments, venous blood samples (~8ml each) will be drawn at 0, 0.33, 0.67, 1, 1.5, 2, 2.5, 3, 4, 6, 9, 12h after fluvastatin dosing. Period 2 will begin after at least a 1-day washout when subjects will receive the second treatment, followed by blood draws at the same time points as after fluvastatin dosing alone.

	Period 1	Period 2
Group 1	A	B
Group 2	B	A

A= fluvastatin; B =rifampin +fluvastatin

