### **15.3 Analysis of Primary Endpoint**

AUC0-∞ will be calculated using the trapezoidal rule from time 0 to Clast + Clast/ke. Parameters such as maximum plasma concentration (Cmax) and time to Cmax (Tmax) will be determined from the observed data. The terminal elimination rate constant (ke) will be obtained using linear regression of log transformed concentrations over the terminal log-linear decline phase. Oral clearance (CL/F) will be calculated using Dose/AUC0-∞. Other estimated pharmacokinetic parameters will be calculated using non-

compartmental methods with WinNonlin Professional software (Pharsight, Inc., Mountain View, CA). Log-transformed pharmacokinetic parameters will be compared across treatments with analysis of variance for repeated measures. Differences will be regarded as statistically significant if  $p < 0.05$ . Data will be presented as mean values with standard deviations. Each subject will serve as his/her own control. Differences in pharmacokinetic parameters between treatments will be calculated using student's paired t-test. Statistical calculations will be done using STATA 10.0 (StataCorporation, College Station, TX).

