#### **15.6 Sample Size and Randomization**

Using a paired t-test and prior data, a sample size of n=10 in each group is needed to detect a 50% difference in AUC $0-12$  between the two study regimens with a statistical power of 80% (two sided alpha = 0.05) and standard deviation of 50%. Due to the lesser effects of rifampin on fluvastatin AUC, the within subject variability can affect the sample size. We plan to enroll sample size of 12 subjects to maintain an adequate sample size in case of potential attrition.

Once included in the study, patients will be randomized using computer-generated random numbers, corresponding to each treatment. This will be performed by someone other than the investigator and will ensure equal number of patients in each treatment sequence.

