## 5. CRITERIA FOR EVALUATION

### 5.1 Primary Efficacy Endpoint

Primary Outcome: The primary outcome will be fluvastatin  $AUC_{(0-12h)}$  and  $AUC_{(0-\infty)}$ .

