## 15.3 Analysis of Primary Endpoint

AUC0-∞ will be calculated using the trapezoidal rule from time 0 to Clast + Clast/ke. Log-transformed pharmacokinetic parameters will be compared across treatments with analysis of variance for repeated measures. Differences will be regarded as statistically significant if p< 0.05. Data will be presented as mean values with standard deviations. Each subject will serve as his/her own control. Differences in pharmacokinetic parameters between treatments will be calculated using student's paired t-test. Statistical calculations will be done using STATA 10.0 (StataCorporation, College Station, TX).

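### Both protocols name two primary AUCs and two tests at p<0.05, with no rule for which result decides

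*Combined protocol and SAP*

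**What the plan says.** The combined document holds two protocols: a single-dose rifampin study, and a second study in subjects whose hepatic enzymes are induced. On this point they read almost alike.

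- **Endpoints.** Section 5.1 of the first protocol says "The primary outcome will be fluvastatin AUC0-12h and AUC0" to infinity. Section 5.1 of the second opens with "Primary Outcome: The primary outcome will be fluvastatin" and lists the same two AUCs. Both synopses agree.
- **Threshold.** The synopsis and section 15.3 of each protocol carry the rule, worded in the second as "Differences will be regarded as statistically significant if p< 0.05". There is no adjustment, and no statement whether one AUC or both must meet it.
- **Tests.** Section 15.3 of each says "Log-transformed pharmacokinetic parameters will be compared across treatments with analysis of variance for repeated measures" and, a few sentences later, "Differences in pharmacokinetic parameters between treatments will be calculated using student's paired t-test". The first gives the log scale but no model terms. The second gives no scale.
- **Design.** Section 4.1 of both describes the work as done "in a two-period, randomized, unblinded, crossover clinical trial", with an AB/BA table.
- **Sample size.** Section 15.6 of both says "a sample size of n=10 in each group is needed to detect a 50% difference in" AUC from 0 to 12 hours, using a paired t-test, 80% power, two-sided alpha 0.05 and an SD of 50%. Twelve subjects are to be enrolled.
- **SAP.** Section 15 of both promises a detailed SAP before the final data are analysed. None of its rules appear in the supplied text.

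**The concern.** With 10 to 12 subjects, one AUC can fall on each side of 0.05, and nothing in the text says which result stands. If either may count, the two-sided 5% error is not held. If both must, the power in section 15.6 does not describe the trial, because it was worked out for one AUC.

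The test has a similar gap. A log-scale ANOVA and a paired t-test can be the same test or different ones, depending on a scale and a period term that the text does not give. The study is unblinded, so these choices could be made after the concentrations are known.

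A supporting reason only: section 1.2 of the second protocol hopes to compare AUC ratios between induced and uninduced states. That is simplest if both protocols use the same AUC and the same log-scale model.

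**Working it through.** **1. The plan's own figure.** Inputs from section 15.6: difference 50%, SD 50%, paired t-test, two-sided 0.05. The standardised paired difference is 50/50 = 1.0, and the noncentrality is 1.0 × √n on n − 1 df. Power is 74.8% at n = 9, 80.3% at n = 10 and 88.3% at n = 12. The stated n = 10 reproduces, provided the 50% is the SD of the paired difference on the same scale as the effect.

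**2. Assumptions.** The documents give no log-scale SD, no correlation between the AUCs and no period effect. I assume:
- a log-difference SD of √ln(1 + 0.5²) ≈ 0.47, which reads 50% as a CV;
- a correlation r of 0.90 to 0.99 between the two AUCs' log differences.

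Section 15.3 says AUC to infinity "will be calculated using the trapezoidal rule from time 0 to Clast + Clast/ke", so it contains the observed AUC plus a tail. If the tail adds independent log variation in each period, the SD it must add is 0.47 × √(1/r² − 1)/√2. That is 0.161, 0.109 and 0.047 for r = 0.90, 0.95 and 0.99. The high correlations are the more plausible.

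**3. Type I error with two AUCs.** Simulated normal log differences, paired t-test at 0.05 for each AUC:

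| r | Either, n=10 | Both, n=10 | Either, n=12 | Both, n=12 |
|---|---|---|---|---|
| 0.90 | 7.25% | 2.73% | 7.19% | 2.81% |
| 0.95 | 6.63% | 3.35% | 6.65% | 3.44% |
| 0.99 | 5.67% | 4.18% | 5.75% | 4.27% |

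The crossover model with a period term gives nearly the same, at most 7.31%. Disagreement between the AUCs at a true ratio of 1 is either minus both: 7.25 − 2.73 ≈ 4.5% at r = 0.90 and 5.67 − 4.18 ≈ 1.5% at r = 0.99.

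**4. Power on the log scale.** True ratio 1.5, so the effect is ln 1.5 = 0.405; crossover model on n − 2 df.

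| | n=10 | n=12 |
|---|---|---|
| One AUC | 66.8% | 76.8% |
| Both AUCs, r = 0.90 to 0.99 | 59.6 to 64.5% | 70.9 to 74.9% |
| AUCs disagree, r = 0.90 to 0.99 | 14.4 to 4.6% | 11.7 to 3.7% |

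Requiring both costs 66.8 − 64.5 = 2.3 to 66.8 − 59.6 = 7.2 points at n = 10, and 1.9 to 5.9 points at n = 12. For one AUC, 80% power needs a log-difference SD of at most 0.40 (n = 10) or 0.45 (n = 12). Over SD 0.35 to 0.60, power at n = 12 runs from 95.0 down to 56.1%. At SD 0.47, 14 subjects give 84.2%.

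**5. The two tests.** With two treatments, a log-scale repeated-measures ANOVA with only subject and treatment has F = t² from the paired t-test on logs, so the p-values are identical. With a period term in the model and no true period effect, paired t and model disagree in about 1.1 to 1.4% of trials at ratio 1. At ratio 1.5 they disagree in 4.8% (n = 10) and 3.2% (n = 12). Power at ratio 1.5, SD 0.47, by assumed period effect in log units:

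| Period effect | Paired t, n=10 | Model, n=10 | Paired t, n=12 | Model, n=12 |
|---|---|---|---|---|
| 0 | 68.1% | 66.8% | 77.6% | 76.8% |
| 0.1 | 66.3% | 66.6% | 76.2% | 76.9% |
| 0.2 | 60.9% | 66.6% | 71.6% | 77.0% |

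**The case against.** The best defence is that the text already points to one analysis. The sample size uses AUC over 12 hours and a paired t-test, the t-test sentence follows the log-transform sentence in the same paragraph, and a SAP is promised. Much of this stands. Reading the t-test as being on logs is natural, and on that reading the two tests agree exactly unless a period term is added. Equal sequence sizes are planned, so a period effect would cost precision and would not bias the paired difference. But a planning input is not a declaration of the deciding endpoint, and the supplied text holds no SAP rule.

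Four stronger readings are tempting, and the documents do not support them:

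- *That no scale is given.* The log scale is stated for the ANOVA in both protocols. Only the t-test sentence lacks one.
- *That the tests necessarily conflict.* They would disagree in about 12 to 17% of trials at ratio 1.5 if the t-test were on raw AUC (between-subject log SD assumed 0.5), but no section says it is.
- *That error approaches the 9.75% of two independent tests.* The AUCs share nearly all their data.
- *That comparing induced with uninduced ratios is an endpoint.* It is a background aim, absent from the second protocol's sections 3.1 and 5.1.

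It is also fair that the protocols expect little transporter effect. Near a ratio of 1 all the disagreement rates are small.

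**Conclusion.** The concern holds as a gap in pre-specification that should be closed. Two primary AUCs without an either/both rule, and two named tests without a rule for which decides, are plain from the text of both protocols. The consequence is moderate. Error exceeds 5% by about 0.7 to 2.3 points if either AUC may count, or power drops by about 2 to 7 points if both must. The AUCs would disagree in about 1.5 to 4.5% of trials at ratio 1 and 4 to 14% at ratio 1.5. The choice between the tests matters less, and not at all if both are on logs without a period term.

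Confidence is high on the missing rule. The sizes rest on an assumed SD of 0.47, correlations of 0.90 to 0.99 and a ratio of 1.5, none of which the documents supply.

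**What to change.** In the synopsis, 5.1 and 15.3 of both protocols, and in the SAP before concentration data are analysed:

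1. Name one deciding AUC and make the other supportive. AUC over 12 hours matches the sample size; if it is chosen, reconcile it with the reference to total exposure in section 3.1 of the first protocol. If AUC to infinity is chosen, redo the sample size for it. Alternatively, require both and give the power for both.
2. Replace the two test sentences with one: log-transformed AUC in a crossover model with subject, period and treatment, reported as the rifampin to no-rifampin geometric mean ratio with its confidence interval. Delete the separate paired t-test.
3. State power on that scale, with the assumed ratio and log-difference SD.

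The cost is mainly wording. The supportive AUC can no longer change the conclusion. The period term costs about 1 point of power with no period effect, gains under 1 point at an assumed shift of 0.1 log units, and gains about 5 to 6 points at 0.2. The restated power may come out below 80%, which would reopen the choice of 12 subjects. This settles which result decides. It does not supply the limit for clinical significance that the objectives in section 3.1 of both protocols also need.

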### **5.2 Secondary Efficacy Endpoints**

Secondary outcomes will include fluvastatin maximum plasma concentration (Cmax) and time to Cmax (Tmax)

### **5.3 Safety Evaluations**

Subjects will be monitored on an ongoing basis while involved with the study by study personnel. Subjects will be screened with a medical history and physical examination by the study physician and have screening hematology, chemistries, liver, renal and coagulation laboratories. Subjects must have normal function of all major organs. At study completion, subjects will have repeat physical examination and repeat hematology, chemistries, liver, renal and coagulation laboratories for safety monitoring. The safety evaluations include change in clinical laboratory finding( Creatinine, phosphokinase) and also the Incidence of adverse events

## **6 SUBJECT SELECTION**

### **6.1 Study Population**

Subjects who meet the inclusion and exclusion criteria will be eligible for participation in this study.

### **6.2 Inclusion Criteria**

1. Healthy male or female, ages 18-65 years old, with no current medical conditions or active diagnoses as determined by the study doctor based on history, physical exam, and laboratory evaluations.
2. Subjects who take no other medications two weeks prior to the study and during the time course of the study including prescription medications, over-the-counter medications, dietary supplements, or drugs of abuse.
3. Subjects able to maintain adequate birth control during the study independent of hormonal contraceptive use (use of condoms).
4. Subjects able to abstain from grapefruit, grapefruit juice, oranges, orange juice, caffeinated beverages and/or alcoholic beverages from 7am the day before the study to completion of that study day.
5. Participants determined to have normal liver and kidney function as measured at baseline (ALT:  $\leq 2x$  upper level of normal (ULN), AST:  $\leq 2x$  ULN, SCr:  $\leq 1.5x$  ULN, T. Bili: 0.1-1.2mg/dL, Albumin: 3.4 – 4.7 mg/dL).
6. BMI between 18.0 - 30 kg/m^2 o Subjects capable of fasting from food and beverages at least 8 hours prior to medication dosing.
7. Be able to read, speak, and understand English.
8. Subjects capable of providing informed consent and completing the requirements of the study.

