### **6.3 Exclusion Criteria**

1. Subjects with active medical problems
2. Subjects on chronic prescription or OTC medication that cannot be stopped 2 weeks prior to and during the study.
3. Subjects incapable of multiple blood draws (HCT < 30mg/dL)
4. Subjects with a history of rhabdomyolysis
5. Subjects with a history of drug-related myalgias
6. Subjects with a history or diagnosis of hemorrhagic tendencies or blood dyscrasias
7. Subjects with a history of GI bleed or peptic ulcer disease
8. Subjects who smoke tobacco or have ongoing alcohol or illegal drug use
9. Subjects who are pregnant, lactating, or trying to conceive during the study period
10. Subjects allergic to fluvastatin or rifampin or any known component of the medications
11. Anyone who in the opinion of the study investigators is unable to do the study

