## **13 PROTOCOL VIOLATIONS**

A protocol violation occurs when the subject, investigator, or sponsor fails to adhere to significant protocol requirements affecting the inclusion, exclusion, subject safety and primary endpoint criteria. Protocol violations for this study include, but are not limited to, the following:

- Failure to meet inclusion/exclusion criteria
- Use of a concomitant medication

Failure to comply with Good Clinical Practice (GCP) guidelines will also result in a protocol violation. The sponsor will determine if a protocol violation will result in withdrawal of a subject.

When a protocol violation occurs, it will be discussed with the investigator and a Protocol Violation Form detailing the violation will be generated. This form will be signed by a Sponsor representative and the Investigator. A copy of the form will be filed in the site's regulatory binder and in the Sponsor's files.

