### **15.1 Data Sets Analyzed**

All eligible patients who are randomized into the study will be included in the data analysis.

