## 6.3 Exclusion Criteria

1. Subjects with active medical problems
2. Subjects on chronic prescription or OTC medication that cannot be stopped 2 weeks prior to and during the study.
3. Subjects incapable of multiple blood draws (HCT  $< 30\text{mg/dL}$ )
4. Subjects with a history of rhabdomyolysis
5. Subjects with a history of drug-related myalgias
6. Subjects with a history or diagnosis of hemorrhagic tendencies or blood dyscrasias
7. Subjects with a history of GI bleed or peptic ulcer disease
8. Subjects who smoke tobacco or have ongoing alcohol or illegal drug use
9. Subjects who are pregnant, lactating, or trying to conceive during the study period
10. Subjects allergic to fluvastatin or rifampin or any known component of the medications
11. Anyone who in the opinion of the study investigators is unable to do the study

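### The albumin range is about 1,000-fold too low and the hematocrit limit has a unit that cannot apply, in the eligibility criteria of both protocols

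*Combined protocol and SAP*

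**What the plan says.** The combined document holds two protocols, one for single-dose rifampin and one for the hepatically induced state. Their eligibility criteria are the same on this point.

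- **Albumin.** Section 6.2 item 5 concerns "Participants determined to have normal liver and kidney function as measured at baseline" and lists limits for ALT, AST, serum creatinine and total bilirubin, ending with "Albumin: 3.4 – 4.7 mg/dL".
- **Hematocrit.** Section 6.3 item 3 excludes "Subjects incapable of multiple blood draws (HCT < 30mg/dL").

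Each limit appears four times: in the synopsis and in Section 6 of each protocol. No other section gives a different unit or a laboratory reference range. Both analytes are on the screening panel in Section 10.1 of each protocol, so every candidate has a result to set against these limits.

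Eligibility then matters in two later places. Section 13 lists "Failure to meet inclusion/exclusion criteria" among the protocol violations. Section 15.1 says: "All eligible patients who are randomized into the study will be included in the data analysis".

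**The concern.** These numbers decide who enters the study; they are not background text. Someone checking source data against the protocol would find an albumin result on a quite different scale from the written range, and a hematocrit result in a unit that cannot be compared with the written limit. They would then have to record a deviation for each subject or reinterpret the criterion without any authority in the text.

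The hematocrit limit also has a protective purpose, since it is attached to the ability to undergo repeated blood draws. Each protocol takes 12 samples of about 8 mL in each of two periods, after a 30 mL draw at screening.

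**Working it through.** **Inputs from the documents.** Albumin 3.4 to 4.7 mg/dL (6.2 item 5). Hematocrit below 30 mg/dL (6.3 item 3). Population: "Healthy male or female, ages 18-65 years old" (6.2 item 1). Sampling: 12 draws per period, two periods, about 8 mL each (4.1), and 30 mL at screening (10.1).

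**Input not in the documents.** Healthy serum albumin of roughly 3.0 to 5.5 g/dL. This is an assumption, kept wide on purpose.

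**Albumin, converted.** 1 g/dL = 1,000 mg/dL, so:

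- 3.4 mg/dL ÷ 1,000 = 0.0034 g/dL
- 4.7 mg/dL ÷ 1,000 = 0.0047 g/dL

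The same digits in g/dL would be 3,400 to 4,700 mg/dL, a factor of 1,000.

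**Albumin, compared with the assumed healthy range.**

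| Assumed albumin | In mg/dL | Ratio to the written upper limit (4.7 mg/dL) |
|---|---|---|
| 3.0 g/dL | 3,000 | 3,000 ÷ 4.7 = 638 |
| 3.5 g/dL | 3,500 | 3,500 ÷ 4.7 = 745 |
| 5.0 g/dL | 5,000 | 5,000 ÷ 4.7 = 1,064 |
| 5.5 g/dL | 5,500 | 5,500 ÷ 4.7 = 1,170 |

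The low end of the assumed range would have to be wrong by a factor of more than 600 before anyone could meet the criterion. The conclusion therefore does not depend on the exact range chosen.

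**Hematocrit, dimensional check.** Hematocrit is cell volume divided by blood volume, a pure ratio reported as a fraction or a percentage. mg/dL is mass divided by volume. No conversion links the two, so a comparison with 30 mg/dL has no answer. The bare number does not fully settle the meaning either: 30 can be a percentage but not a fraction, which cannot exceed 1.

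**Blood volume behind the hematocrit criterion.** 12 × 2 = 24 samples; 24 × 8 mL = 192 mL; 192 + 30 = 222 mL, before the laboratory tests at study completion.

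**Consequence on a literal reading.** Every volunteer's albumin exceeds 4.7 mg/dL, so every enrolled subject fails criterion 5. Each is then a protocol violation under Section 13. None is eligible, so none belongs to the set that Section 15.1 defines.

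**Extraction error?** Unlikely. Each unit recurs in four places across two separately typeset protocols.

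**The case against.** The strongest reply is that these are evident slips. The bilirubin limit immediately before albumin in the same list is also in mg/dL, so the albumin unit may simply have been carried over, though that is inference. Clinical staff would probably read both limits as intended, and no endpoint, sample size or analysis method depends on them. This stands, and it keeps the point minor.

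Three stronger readings are tempting, and the documents do not support them.

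- **That both units are impossible.** A reader might infer this, but mg/dL is a legitimate mass-concentration unit for albumin. The fault there is scale. Only the hematocrit unit is invalid.
- **That subjects lose their protection against excessive blood sampling.** The hematocrit value is a parenthesis after "Subjects incapable of multiple blood draws", and those words can still be applied by judgement. Section 6.2 item 1 requires a study doctor's finding of good health based partly on laboratory results. Section 6.3 items 6 and 11 exclude blood dyscrasias and anyone the investigators judge unable to take part. Section 5.3 requires normal function of all major organs. What is lost is a numeric cut-off.
- **That subjects will in fact be withdrawn, or the analysis set will be empty.** This follows only if the text is applied literally, which is unlikely. Even then withdrawal is not automatic, because Section 13 leaves that decision to the sponsor.

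What survives is that the text is wrong at two decision thresholds in both protocols, and that nothing elsewhere corrects it.

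**Conclusion.** The point holds as a minor correction. The albumin range is about 1,000-fold too low as written. The claim that it admits no volunteer rests on the assumed healthy range of roughly 3.0 to 5.5 g/dL and holds for any plausible alternative. The hematocrit cut-off cannot be evaluated in its stated unit; this needs no assumption beyond the definition of hematocrit. The expected practical effect on enrolment and analysis is small. The violation and analysis-set consequences belong to the literal reading and should not be presented as the likely course of the trial.

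**What to change.** In each protocol, correct the units in Section 6.2 item 5, Section 6.3 item 3 and the synopsis to those the site laboratory reports: a mass concentration at the right scale for albumin, and a stated percentage or fraction for hematocrit. The sponsor should confirm the intended limits; this review proposes no values.

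The cost is a minor amendment to each protocol, submitted to the IRB. Section 17.1 requires written approval before an amendment is implemented. Section 17.2 makes an exception for purely logistical or administrative changes, but a correction to eligibility limits may not qualify, so submission should be assumed. Design, power and analysis are unaffected.
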